Brief Addiction Monitor-Revised (BAM-R)¹⁰⁰⁻¹⁰¹ is a 17-item self-report measure developed by researchers at the Philadelphia Veterans' Administration Medical Center to assess symptoms of Substance Use Disorder. The BAM-R can be scored using a three-factor structure (substance use severity, risk factors, and protective factors) and shows reliability and validity in Veteran samples (Duration: 5 minutes). **Adult Suicidal Ideation Questionnaire** (ASIQ)⁹² is a 25-item self-report measure of suicidal ideation that will be used to assess changes in suicidal ideation. Reliability and validity have been demonstrated in clinical and community samples⁹³ (Duration: 10 minutes). **The Expressions of Moral Injury Scale (E-MIS)**⁸⁷ is a 17-item self-report scale that is used to measure expressions of moral injury related to how experiencing morally injurious events may affect one's emotional well-being, relationships and quality of life. The E-MIS measures self-directed (e.g., "I am ashamed of myself because of things I did/saw during my military service") and other-directed (e.g., "I feel anger over being betrayed by someone who I had trusted while I was in the military") subtypes of moral injury. (Duration: 7 minutes). The **Global Ratings of Change Scale (GC)** is a 6-item scale developed for the proposed study to assess self-report change following the interventions (e.g., "my current ability to live consistently with my values is _____ than my ability to live consistently with my values before I enrolled in the study."). The GC uses a 15-point Likert-type rating scale ranging from -7, "a great deal worse," to +7, a great deal better. The GC follows guidelines for an anchor-based approach to determining the minimally clinically important difference.³⁴ (Duration: 3 minutes; Administration: Post-Treatment, One-month follow-up, Three-months follow-up).

B. Description of Population to be Enrolled:

All data will be collected from eligible and willing Veterans that meet the following eligibility criteria:

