Description of Treatment Conditions. Description of Treatment Conditions. *Present Centered Therapy (PCT-MI)*. See p. 6 of this protocol for a description of PCT-MI. ***Acceptance and Commitment Therapy for Moral Injury (ACT-MI)***. See p. 4-5 of this protocol for a description of ACT-MI.

Measures:

The following measures were selected based on their content validity and other psychometric properties. **Descriptive Measure.** The ***Rocky Mountain MIRECC Demographics Form*** will be used to assess demographic variables such as age, sex, and ethnicity, as well as variables related to education, employment, housing, and military history (*Duration:* 5 minutes; *Administration:* Baseline assessment).

Safety Monitoring Measure. The ***University of Washington Risk Assessment Protocol (UWRAP)***⁷¹ is a structured clinical interview that evaluates participants' acute emotional state prior to the study and capacity to complete the study procedures. At the end of the study, the UWRAP debriefing protocol will be initiated (See Appendix 1). Members of the research team will evaluate responses and access additional assistance as necessary (*Duration:* 10 minutes; *Administration:* All Assessments).

Baseline measures to diagnostically characterize the sample: To characterize the sample at baseline the Structured Clinical Interview for the DSM-5 and the Columbia-Suicide Severity Rating Scale will be administered. ***Structured Clinical Interview for DSM 5 Research Version (SCID-5-RV)- Modules A, D, E, F, and L*** is a diagnostic interview used to determine DSM-5 disorders. All participants will be administered the SCID-5-RV during the baseline assessment session. Specifically we will administer the following modules: A- Mood Episodes, D- Differential Diagnosis of Mood Disorders, E- Substance Use Disorders, F- Anxiety Disorders, and L- Trauma- and Stressor-related Disorders. This will provide a broader diagnostic characterization of the participants.

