Approximate time to complete: 30 minutes; Administration: Baseline. ***The Columbia-Suicide Severity Rating Scale (C-SSRS)*** (Posner, Brown, Stanley, Brent, Yershova, Oquendo, Currier, Melvin, Greenhill, Shen, & Mann 2011): The C-SSRS is a clinician-administered measure that assesses for suicidal ideation and attempt behavior based on established definitions. The C-SSRS assesses intensity of suicidal ideation, specifically asking about frequency, duration, intrusiveness, controllability, and deterrents, as well as suicide-related behavior, such as actual attempts and aborted attempts. *Approximate time*

to complete: 10 minutes; Administration: Baseline. **Moral Injury Outcome Scale (MIOS)** (Lits, Phelps, Frankfurt, Murphy, Nazarov, Houle, Levi-Belz, Zerach, Dell, Hosseiny & members of the *Moral Injury Outcome Scale Consortium* 2021): The MIOS is a 32-item self-report measure used to assess the type of morally injurious event experienced, as well as the extent to which that event has affected functioning. The MIOS assesses the impact a morally injurious event has had on trust, guilt, self-doubt, and faith in relation to the self, others, and spiritual practices. *Approximate time to complete: 10 minutes; Administration: Baseline.*

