We will recruit across outpatient clinics, community based outpatient clinics, and Veteran centers. We will request referrals from clinicians in the PTSD Clinical Team (PCT), Substance Abuse Treatment Program (SATP), and Mental Health Clinic ([name] is a clinician in the PCT-MI and SATP) and other providers who might have contact with Veterans with moral injury. In addition to clinician referrals, we plan to utilize targeted recruitment mailings. Using the VA-DoD Identity Repository (VADIR), VA corporate data warehouse (CDW), and VA electronic medical records (e.g., CPRS, JLV, VISTA, TIU) we will mail discrete invitation letters to Veterans who were active during military conflicts, have been diagnosed with disorders often associated with moral injury (e.g., PTSD, depression, substance use) or have a history of suicidal behaviors (e.g., Suicide Behavior Report Notes), or whose medical records indicate other variables potentially related to exposure to morally injurious events. The discrete invitation to participate in the research, an informal flyer, and a pre-addressed and postmarked Opt Out/In postcard will be mailed to Veterans. Veterans can use the Opt Out/In postcard to indicate that they do not wish to receive additional mailings about this study or that they would like to be called by a study team member. Two additional reminder letters may be sent to potential participants who neither indicate interest in the study nor return the Opt Out/In card. Veterans who indicate interest in the study will be contacted, provided specific details about the study, and- if still interested in participation- be screened for study eligibility.

Enrollment:

Informed Consent. Participation will be voluntary, and potential participants will have ample time to review the postcard consent with trained staff and to ask questions about the study. Research staff will assess patients' understanding of the postcard consent, based on whether they can adequately respond to the following questions about the study:

- 1) *What are you being asked to do?*
- 2) *Finish this sentence - The purpose of this study is to find out...*
- 3) *True or False: After beginning this study, you can decide not to continue at any time, without penalty.*
- 4) *What should you do if you have questions about this study?*
- 5) *Who should you call if you feel you have been harmed in this study?*
- 6) *What are the risks of participating in this study?*

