- 7) *What are the benefits of participating in this study?*

Veterans who cannot adequately answer these questions will be excluded from participating.

Participants will have had the option during the screening and verbal consent to receive text message PHI/PII-free text message reminders for their baseline appointment. During the baseline appointment consent process, participants will select their reminder and scheduling preferences for the one- and three-month follow-up appointments. Participants will receive reminder phone calls and letters. They will select the level of detail that can be used for the reminder phone calls (please see consent form for details). As in COMIRB #15-0346, #16-0350, and #17-0603 participants will also be given the option of receiving text message reminders stating "REMINDER: You have a research appointment on [month, day, year] at [time]. Please call [contact phone number] if you have any questions." If the study team has been unable to reach a participant to schedule or reschedule a follow-up appointment, the participant will be sent a text message stating "REMINDER: Please contact our research coordinator to schedule your appointment [contact phone number]." Text messages will not contain PII or PHI.

Protected Health Information (PHI). PHI to be collected may include: first and last name, date of birth, mailing address, and full social security number. This information is needed to access participants' medical records to collect data for this study. Additional PHI will include demographic information (including military history), use of VA services, and medical and mental health history.

Authorization Procedures. A waiver of consent and a HIPAA Waiver of Authorization is being requested for the entire study. This will allow members of the research team to view medical charts of potentially eligible patients. The medical records will be reviewed to screen potential participants to determine study eligibility and appropriateness to participate in the intervention. Review of the medical records also allows members of the research team to screen for other criteria that would exclude participation (e.g., safety-related issues, psychiatric distress) and reduce burden on ineligible patients. The consent and HIPAA waiver will also allow study participants to complete the study online when face-to-face sessions are not able to be offered.

V. Description, Risks and Justification of Procedures and Data Collection Tools:

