Another barrier that was apparent in reviewing the literature was in the measurement of moral injury. To address this barrier our team developed a moral injury interview to help facilitate screening for Veterans to ensure appropriateness for participation in the study. We are taking a multidimensional approach to assessing moral injury to ensure that our measures are sensitive enough to capture changes in functioning. We will be administering measures related to ACT processes repeatedly (e.g., AAQ-II, MEAQ-30) over the course of treatment to help determine which measures might be most sensitive to change over time for a future efficacy trial. Additionally, we will be using EMA via the implementation of a mobile application to measure changes associated with functional outcomes and ACT processes in a more ecologically valid manner. We have consulted with an expert in EMA who has previously collaborated with the Palo Alto VAMC to identify how to utilize a mobile application to detect changes in moral emotions, experiential willingness, and behavioral activation ([name]). EMA procedures have been successfully applied to measuring in the moment changes in emotions in Veterans⁹⁴ and have also been used to assess experiential avoidance and shame, indicating the relevance and feasibility of this methodology to the goals of the present study.⁹⁴⁻⁹⁵ Please see the "measures" section for more details about EMA procedures.

VII. Data Analysis Plan:

Data Analysis & Methodological Considerations. Analyses will be descriptive in nature, although variability and precision estimates (95% confidence intervals) will be provided for

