acceptability and feasibility summary statistics. Results will be presented across participants and individually for each group. **Sample Size.** Areán and Kraemer recommend sample sizes between 50 and 100 to generate variability estimates for outcome measures and to facilitate a “dress rehearsal for the clinical trial” (p. 95).¹⁷ As this trial serves as a precursor to a larger scale efficacy study and one of our goals is to determine the fit of candidate outcome measures, we will enroll 36 participants per condition (72 participants total) to account for attrition. As a method of data analysis for qualitative measures, thematic content analysis will be used as an iterative process of interpretation for the purposes of scoring, coding, and seeking patterns (themes) across verbal materials so that inferences about characteristics of a group can be generated.^{97, 5} First, data will be recorded and coded without identifiers. Reviewers will independently code interviews. Each interview will be coded by at least two reviewers. Reviewers will independently identify themes among codes. Reliability and validity among themes between reviewers will be determined in a consensus meeting. In the consensus meeting the coding team will define and name the themes that best represent the narratives from the individual interviews. This process is consistent with previous qualitative research conducted on moral injury.⁵

Aim 1: Evaluate the acceptability of the ACT-MI intervention for Veterans experiencing impairment in functioning associated with moral injury. We will assess the proportion of participants who find ACT-MI acceptable, defined as $\geq 70\%$ of participants scoring ≥ 24 on the Client Satisfaction Questionnaire (CSQ).¹⁹ The Narrative Evaluation of Intervention Interview (NEII)²⁰ will be used to inform any necessary revisions to the intervention and refinement of the treatment manual. Qualitative data collected using the NEII will be used to understand the limitations and strengths of the interventions via thematic content analysis. If fewer than 70% of participants find ACT-MI or PCT-MI acceptable, the qualitative data will be examined to determine areas for improvement.²⁰

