Aim 2: Determine the feasibility of the efficacy study design. Feasibility will be assessed by examining the following outcomes related to recruitment, retention, and provider adherence **a) Participant recruitment rates.** The number of participants approached for the study who are eligible to participate and of those, the number who enroll in the study (i.e., willingness to participate) will be evaluated. Feasibility will be defined as $\geq 50\%$ eligible and of these $\geq 30\%$ willing to participate in the proposed time frame. **b) Participant Retention.** Participant completion of ACT-MI will be measured by the percentage of participants who complete treatment and receive an adequate dose (completed a minimum of 70% of the intervention). Reasons for termination will be examined via the RT-C/T. The percentage of participants lost to follow up (LTFU) will be calculated as the percentage of participants who fail to complete one-month and three-month follow-up visits, with $\leq 30\%$ LTFU considered feasible. This will inform the necessary sample size and treatment retention strategies for future studies. **c) Provider adherence.** To examine the extent to which ACT-MI can be delivered as intended ($\leq 15\%$ of deviations for each clinician across participants on the treatment fidelity checklist), the proportion of sessions in which each clinician achieved acceptable fidelity out of all of the clinician’s sessions will be reported for all study clinicians. Qualitative review of fidelity checklists will be used if treatment fidelity is less than desired and areas of difficulty will be identified to inform training procedures for clinicians and treatment manual revisions.

Aim 3: Select measures and calculate necessary sample size for a future efficacy study. Evaluate candidate measures based on the following factors: (1) Amount of missing data and its distribution for all measures across groups; (2) means, standard deviations, and 95% confidence

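### After randomisation, no scheduled instrument is described as asking about suicide attempts, so the pilot has no systematic count of suicidal behaviour by arm

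*Combined protocol and SAP*

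**What the plan says.** Section IV.C, Measures, places the C-SSRS among the instruments that describe the sample at entry: "To characterize the sample at baseline the Structured Clinical Interview for the DSM-5 and the Columbia-Suicide Severity Rating Scale will be administered". The same entry says that the scale covers ideation "as well as suicide-related behavior, such as actual attempts and aborted attempts" and gives its administration as baseline. In Section IV.C, Procedures, it is in the baseline battery and in neither the post-treatment list nor the list shared by the one- and three-month follow-ups.

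Two suicide-specific tools continue. The ASIQ "is a 25-item self-report measure of suicidal ideation that will be used to assess changes in suicidal ideation" (Section IV.A, Measures of Psychopathology). The UWRAP is stated for all assessments (Section IV.C, Measures). Appendix 1 prints its items: present stress, urge to self-harm, intent to kill oneself, and urge to use substances, each from 1 to 7.

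Section II names suicidal ideation and behaviour among the risks heightened by morally injurious events. Section IV.C, Recruitment, lists several alternative grounds for an invitation letter, one being Veterans who "have a history of suicidal behaviors (e.g., Suicide Behavior Report Notes". The only suicide-related exclusion is imminent risk (Section IV.B). On records, Section IV.C, Authorization Procedures, says: "A waiver of consent and a HIPAA Waiver of Authorization is being requested for the entire study".

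**The concern.** The plan identifies suicidal behaviour as a consequence of the condition under treatment and is willing to invite people who have shown it. It then follows ideation and present risk over time, but not behaviour. Someone who made an attempt between two visits and is calm at the next could give the lowest score on both UWRAP suicide items, and nothing in the described batteries would then ask.

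At stake is what the pilot can tell the planners of the efficacy trial. The study is meant as a rehearsal and has choosing measures as an aim. Followed exactly, the schedule yields no systematic count of suicidal behaviour after randomisation, overall or by arm, and does not test whether such a count can be collected.

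**Working it through.** **Sample size.** "we will enroll 36 participants per condition (72 participants total) to account for attrition": 2 × 36 = 72, as stated. Section VII says "Analyses will be descriptive in nature, although variability and precision estimates (95% confidence intervals) will be provided for" the acceptability and feasibility summaries. No alpha, power or effect size is given, so there is no sample-size calculation to check. The point turns on the schedule.

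**Schedule, from Section IV.C (Measures and Procedures) and Appendix 1.**

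| Instrument | Content as described | Baseline | Post-treatment | One month | Three months |
|---|---|---|---|---|---|
| C-SSRS | Ideation; attempts and aborted attempts | Yes | No | No | No |
| ASIQ | Ideation | Yes | Yes | Yes | Yes |
| UWRAP | Present stress, urge, intent | Yes | See note | See note | See note |

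Note: Measures gives the UWRAP at all assessments, but the post-treatment and follow-up lists in Procedures omit it, and follow-up may be completed by survey link or mail. These passages need reconciling.

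In Section IV.A, the Aim 3 paragraph opens by saying that its measures are given at all four points, and the C-SSRS comes under that aim. Its own subheading there, the administration line in IV.C and the Procedures lists all confine it to baseline. Behaviour is therefore assessed at 1 of 4 points, and at 0 of 3 after randomisation.

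**Other routes to an attempt.**
- The UWRAP risk worksheet is completed by a clinician only when a score or signs of distress call for it (Appendix 1). Its content is not in the documents.
- Adverse-event reporting relies on the participant contacting the investigator. The definition is limited to events directly related to participation, during testing or treatment or within two weeks of it (Section V, Adverse events).
- Record review is described chiefly for eligibility. No extraction after randomisation is scheduled.

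**Scale.** The documents give no attempt risk, so p below is an assumed risk per participant over the study. The chance of at least one attempt among n is 1 − (1 − p)^n.

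| Assumed p | n = 36 (one arm) | n = 72 |
|---|---|---|
| 1% | 30.4% | 51.5% |
| 2% | 51.7% | 76.7% |
| 3% | 66.6% | 88.8% |
| 5% | 84.2% | 97.5% |

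With complete ascertainment and no events, the exact two-sided 95% upper limit is 1 − 0.025^(1/n): 9.7% for n = 36 and 5.0% for n = 72. Those limits apply only if the zero is a true zero, which the present schedule cannot establish.

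**The case against.** The strongest reply is that the plan does monitor suicide risk throughout. Appendix 1 applies the UWRAP before measures or an intervention session, and Section V, Safety Monitoring, adds a debriefing after assessment or treatment sessions. Formal risk assessment can be set off by ideation on the UWRAP, by other statements, or by answers on other measures, which would include the ASIQ. This stands. A reader might infer that suicide monitoring ends at baseline, or that an attempt becomes known only if the participant volunteers it; the documents support neither. The ASIQ items and the UWRAP worksheet are not reproduced, so the claim is limited to what the instruments are described as asking.

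A reader might also infer that the pilot will be unable to report suicidal behaviour. That goes too far. Section IV.C, Protected Health Information, says records are accessed to collect study data, and the records could still be queried after follow-up ends. The information is unplanned, not lost.

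Nor does the 30% tolerance for loss to follow-up give a number without any interview. Section VII defines the loss by two visits only: "The percentage of participants lost to follow up (LTFU) will be calculated as the percentage of participants who fail to complete one-month and three-month follow-up". So 72 × 0.30 = 21.6 may include people who attended the post-treatment session. Conversely, people who are retained may answer by survey or mail and never be interviewed.

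Finally, recorded suicidal behaviour is one of several alternative mailing criteria, not an inclusion criterion, and Section VI describes direct mailing as a step to take if needed. No expected share is given, so the sample cannot be called one selected for suicidal behaviour. Comparing safety is not among the five aims, and 36 per arm could say little about relative risk. Both points limit the weight of the concern, but neither supplies the missing count.

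**Conclusion.** The concern holds as a gap in measurement. The only instrument described as recording attempts is used once, before randomisation, and no later scheduled instrument is described as asking about attempts since the last contact. Triggered clinician assessment may reveal some attempts, but that depends on presentation on the day and does not give counts comparable between arms. All 72 planned participants are affected.

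The probabilities above rest on assumed risks and show only that one or more attempts would not be surprising. The conclusion itself rests on the schedule as written and on the short descriptions of the ASIQ and UWRAP; it would soften if the full instruments turned out to ask about interval behaviour of every participant. The acceptability and feasibility aims are untouched. This is an inexpensive improvement to what the pilot can report, not a flaw in its main purpose.

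**What to change.** Pre-specify extraction of Suicide Behavior Reports from the VA record for every randomised participant (72 planned), including those lost to follow-up, from randomisation to three months after treatment. Define the end date for people who stop early, for example by the last scheduled session of their assigned group. Tabulate the counts descriptively by arm. The plan already names this source for recruitment; the stated purpose of the waiver should be extended to cover this use.

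Where a post-treatment or follow-up visit is already led by an interviewer, the C-SSRS behaviour items, asked since last contact, may be added. Survey and mail responders would be covered by the record query only, so the report should show the two sources separately. The Measures and Procedures passages on the UWRAP should be reconciled in the same amendment.

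The cost is a protocol amendment, one record query per participant, and up to 10 minutes per interviewer-led visit (the time the protocol gives for the C-SSRS). The sample size does not change. The query would still miss attempts unknown to the VA, and with 36 per arm the table supports description, not comparison.
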